3.1.1 Phase 1b (Dose Escalation)

During the dose escalation portion of the study, dosing will be based on assigned cohort. Approximately 25 patients are expected to enroll in this phase. Cohort size will be up to 7 patients using a conventional modified 3+3 design for dose escalation studies in oncology.

On Cycle 1 Day 1, in an effort to ensure that patients tolerate oral valganciclovir prior to receiving nanatinostat, valganciclovir will be taken first, followed by nanatinostat approximately 1 hour later. For all subsequent administrations, the sequence of nanatinostat and valganciclovir can be dictated by patient convenience (e.g., both drugs may be taken together if tolerated by the patient). With the implementation of Protocol Amendment 4.0, nanatinostat and valganciclovir will be taken together at all timepoints, including Cycle 1 Day 1.

The first cycle is defined as the dose-limiting toxicity (DLT) assessment period. Grading of DLTs will be according to the National Cancer Institute Common Terminology Criteria for Adverse Events (NCI CTCAE) version 5 and detailed in Section 3.1.5 of the protocol as well as [Section 3.4.1](#) of the SAP. Patients who are unable to complete the DLT assessment period for reasons other than study drug-related toxicity may be replaced if needed to achieve at least 3 patients evaluable for DLTs.

A Safety Review Committee (SRC) comprised of study investigators, the study medical monitor and a Sponsor representative will govern the conduct of the study, and will have the option of defining additional cohorts and doses either below, above, or intermediate to the planned doses as needed based on data generated from prior cohorts. The SRC may also modify the dosing schedule for either nanatinostat or valganciclovir as required to accommodate different dosage strengths and patient convenience. However, when the schedule is adjusted, the total daily dose will remain unchanged. The Phase 1b planned doses for each cohort are provided in Table 2.

Table 2 Phase 1b Dose Levels by Cohort

Cohort Number	Dose Nanatinostat	Dose Valganciclovir
1	10 mg BID (20 mg daily dose)	900 mg BID
2a	5 mg BID (10 mg daily dose)	450 mg BID
2b	10 mg QD (10 mg daily dose)	450 mg BID

Cohort Number	Dose Nanatinostat	Dose Valganciclovir
2c	10 mg QD (10 mg daily dose)	900 mg QD
3	20 mg QD (20 mg daily dose), 4 days on and 3 days off in a 7-day regimen	900 mg QD

BID, twice daily; QD, once daily.

3.1.2 Phase 2 (Dose Expansion)

The phase 2 dose expansion portion of the study will evaluate the RP2D in 30 patients with relapsed/refractory EBV⁺ lymphomas. This sample size is based on a Simon's 2-stage design where the Phase 2 portion of the study may be stopped if none of the first 10 treated patients have a response.

The dose and schedule of nanatinostat and valganciclovir used during the Phase 2 portion of the study will be the RP2D for nanatinostat and valganciclovir as determined by the SRC at the conclusion of the Phase 1b portion of the study. A Core SRC consisting of 2 investigators and 1 clinical expert appointed by the Sponsor will assess the toxicity during the phase 2 dose expansion and modify the dosing schedule of nanatinostat and/or valganciclovir as appropriate. Changes to the schedule will be enacted with minimal or no change to the total daily dose. Patients who are unable to complete at least one disease assessment to evaluate efficacy during the Phase 2 portion of the study may be replaced.

In both phases, patients will continue to receive nanatinostat/valganciclovir if, in the opinion of the Investigator, the patient is still receiving clinical benefit, the patient does not demonstrate progressive disease (in the absence of clinical deterioration, patients may continue on study drug until a repeat scan confirms progression), and in the absence of unacceptable toxicity.

3.1.3 Tablet Cohort

Once the Phase 2 arm has completed enrollment, approximately 10 patients will be enrolled into a cohort to receive nanatinostat tablets instead of capsules. The dose and schedule of nanatinostat and valganciclovir administered to patients in the tablet cohort will be the RP2D. With exceptions as described in the protocol, patients will follow the protocol/assessments as detailed for the Phase 2 expansion cohort patients.

3.1.4 Other Aspects of the Study Design

Exploratory biomarkers will be evaluated in this study as indicated in the schedule of events (Table 15) in the clinical study protocol. Archived blood, PBMCs, plasma, and/or tissue samples may be used for assessment of other exploratory biomarkers (if identified).

The End of Treatment (ET) Visit is the visit at the time of study treatment discontinuation. If the decision is made to discontinue study treatment outside of a

scheduled visit, an attempt will be made to have the patient return for an ET visit. Safety will be assessed at the Safety Follow-Up Visit, approximately 28 days following the final administration of nanatinostat/valganciclovir.

Survival and follow-up assessment will be conducted at least every 3 months for assessment of new antitumor therapy, disease progression status, and survival following the safety follow-up assessment. This assessment may be conducted by review of the patient records or by patient contact (e.g., telephone, email). Patients who are unable to be contacted following at least three attempts (one of which is contact by registered mail) will be considered lost to follow-up.

3.2 Schedule of Assessments

For the complete schedule of assessments, refer to Section 7 (Table 15, Schedule of Events) in the clinical study protocol.

3.3 Treatments

3.3.1 Treatments Administered

3.3.1.1 Nanatinostat

Nanatinostat is a hydroxamic acid-based histone deacetylase (HDAC) inhibitor. Nanatinostat drug product is currently supplied as 5 mg strength capsules and 10 mg film-coated immediate-release tablets were introduced in this study with amendment 5. The comparability between the tablets and capsules has been established via in vitro dissolution studies and in vivo dog pharmacokinetic studies.

Nanatinostat capsules will be administered in the Phase 1b portion of the study at a dose and schedule determined by the assigned cohort. In the Phase 2 portion of the study, patients will receive nanatinostat at the RP2D (nanatinostat 20 mg daily, Days 1 through 4/7 per week and valganciclovir 900 mg daily) and schedule determined in the Phase 1b portion of the study.

For the approximately 10 patients in the tablet cohort, patients will receive nanatinostat tablets rather than capsules. The dose and schedule of nanatinostat administered in the tablet cohort will be the same used with capsules in the Phase 2 portion of the study.

3.3.1.2 Valganciclovir

Valganciclovir (VALCYTE[®]), an oral prodrug of valganciclovir, is a cytomegalovirus (CMV) nucleoside analogue DNA polymerase inhibitor. In the Phase 1b portion of the study, the starting dose of valganciclovir will be determined by assigned cohort. In the Phase 2 portion of the study (including the tablet cohort), the starting dose and schedule of valganciclovir will be at the RP2D determined by the SRC at the conclusion of the Phase 1b portion.

3.3.2 Method of Assigning Patients to Treatment Groups

This is an open-label study that consists of a dose-escalation phase, followed by a dose-expansion phase. There will be no blinding. Patients in the dose-escalation phase will

be enrolled in cohorts based on recommendations by the SRC. Patients in the dose expansion phase and tablet cohort will receive the RP2D determined at the conclusion of the Phase 1b portion.

3.4 Safety and Efficacy and Safety Variables

3.4.1 Safety Variables

Safety assessments consist of monitoring and recording all AEs, regular laboratory evaluation for hematology, blood chemistry, coagulation and urinalysis, periodic measurement of vital signs, electrocardiograms (ECGs), performance status and physical examinations.

3.4.1.1 Primary Safety Endpoints

An AE is any untoward medical event that occurs in a patient following the start of investigational product (IP) administration, whether the event is considered IP-related or not. Pre-existing conditions are not considered an AE unless the condition worsens by at least 1 grade following the start of IP administration. Adverse events will be captured with the first dose of study drugs (on Cycle 1 Day 1) and continue until 28 days after the last dose of study drugs or until a new anticancer treatment is started whichever is first.

Dose-limiting toxicity AEs must meet all of the following criteria:

- Occurs during the first cycle (28 days) of study drug administration in Phase 1b only
- Is not incontrovertibly related to underlying disease
- In addition, to be considered a DLT, the AE will meet at least one of the criteria listed below:
 - Grade 4 anemia unexplained by underlying disease
 - Grade 4 febrile neutropenia
 - Grade 4 neutropenia lasting >5 days
 - Any other Grade 4 hematologic toxicity (thrombocytopenia, neutropenia, febrile neutropenia, anemia) of any duration
 - Grade 4 or higher tumor lysis syndrome
 - Grade 3 or higher thrombocytopenia (with or without bleeding)
 - Any requirement for platelet transfusion
 - Grade 3 or higher non-hematologic toxicity despite adequate supportive care
 - Results in a dose hold of >7 consecutive days

AEs that persist <72 hours and are able to be managed with supportive care may be excluded.

3.4.1.2 *Secondary Safety Endpoints*

Laboratory Parameters

Clinical laboratory evaluations will follow those outlined in the clinical study protocol and will be performed using a central or local laboratory. Evaluations include hematology, chemistry, urinalysis, coagulation, and pregnancy tests (for women of childbearing-potential only). Specific parameters to be collected are listed below:

- Hematology (blood): Complete blood count with differential to include white blood cells and differential, red blood cells, hemoglobin, hematocrit, platelets, mean corpuscular hemoglobin, mean corpuscular volume
- Chemistry (blood): Sodium, potassium, chloride, bicarbonate, blood urea nitrogen, creatinine, glucose, calcium, phosphate, magnesium, aspartate aminotransferase (AST), aminotransferase, alanine aminotransferase (ALT), total bilirubin, alkaline phosphatase, total protein, albumin, uric acid, and lactate dehydrogenase
- Coagulation (blood): prothrombin time, partial thromboplastin time, and international normalized ratio
- Urinalysis (urine): color, appearance, glucose, bilirubin, ketone, specific gravity, blood pH, protein, urobilinogen, nitrite, leukocyte esterase, red blood cells, white blood cells, epithelial cells

Electrocardiograms

Electrocardiograms will be performed as outlined in the clinical study protocol. When performed on days that include PK draws, ECGs will be performed prior to or as close as possible to the PK draw. For days when there are no scheduled PK draws, the ECG will be performed at any time during the clinic visit, irrespective of the time of study drug dosing. Prior to each ECG, the patient will lie in a supine position in a calm environment for at least five minutes. For patients enrolled under protocol amendment 5.0, triplicate assessments no more than five minutes apart are required for the following times:

- Screening
- Cycle 1 Day 1 pre-dose
- Cycle 1 Day 2 pre-dose and post-dose at 2 hours
- Cycle 1 Day 15 pre-dose and post-dose at 2 hours
- Cycle 2 Day 1 pre-dose and post-dose at 0.5, 1, 2, 4, and 6 hours
- Cycle 2 Day 15 pre-dose and post-dose at 2 hours

At times not listed above, single ECGs will be performed. On study days requiring a single ECG, if ECG indicates an increased QTcF interval, two additional ECGs will be performed at least two minutes apart.

Vital Signs

Vital signs, including weight, heart rate, respiratory rate, blood pressure, temperature, and oxygen saturation by pulse oximeter, will be collected as outlined in the clinical study protocol. On Cycle 1 Day 1, measurements will be collected prior to first dose of valganciclovir and nanatinostat and PK draws. For all other regularly scheduled visits, measurements will be collected prior to administration of study drugs.

Other Safety Variables

Physical exams will be performed at the screening visit only; symptom-directed physical exams will be conducted at each visit through Safety Follow-up as outlined in the clinical study protocol. Performance status will be measured by either the Eastern Cooperative Oncology Group (ECOG) or Karnofsky Performance Scale (KPS) and will be regularly evaluated as outlined in the clinical study protocol.

Plasma CMV DNA levels were monitored for 12 months by qPCR.

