3.1.5. Dose Limiting Toxicity

Grading of DLTs will be according to the National Cancer Institute Common Terminology Criteria for Adverse Events (NCI CTCAE) version 5.

To be considered a DLT, an AE must meet all of the following criteria:

- Occurs during the first cycle (28 days) of study drug administration in Phase 1b only
- Is not incontrovertibly related to underlying disease

In addition, to be considered a DLT, the AE will meet at least one of the criteria listed below:

- Grade 4 anemia unexplained by underlying disease
- Grade 4 febrile neutropenia
- Grade 4 neutropenia lasting >5 days
- Any other Grade 4 hematologic toxicity of any duration
- Grade 4 or higher tumor lysis syndrome
- Grade 3 or higher thrombocytopenia (with or without bleeding)
- Any requirement for platelet transfusion
- Grade 3 or higher non-hematologic toxicity despite adequate supportive care
- Results in a dose hold of >7 consecutive days

Adverse events may be excluded from the definition of DLT if they meet the following criterion:

- AEs that persist <72 hours and are able to be managed with supportive care

The SRC ([Section 3.10](#)) will have the option of declaring other toxicities, not listed above, as DLTs if necessary to ensure patient safety.

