4.5.2 Adverse Events

Treatment-emergent adverse events (TEAEs) are defined as those adverse events (AEs) with onset after the first dose of study drug or pre-existing events that worsened by at least one grade after the first dose during the study. Treatment-emergent AEs will be summarized by study phase and cohort. Events reported with a partial onset date (e.g., month and year are reported but the day is missing) will be considered to be treatment-emergent if it cannot be confirmed that the event onset was prior to the first dose of study drug based on the available date entries.

Verbatim terms on case report forms will be mapped to preferred terms and system organ classes using the Medical Dictionary for Regulatory Activities (MedDRA, version 25.0). As an additional safety analysis, certain hematological AEs will be programmatically re-mapped to preferred terms and system organ classes consistent with CTCAE v5.0 categories. Select AE summaries will be repeated using this alternative mapping.

Summaries that are displayed by system organ class and preferred terms will be ordered by descending incidence of system organ class and preferred term within each system organ class. Summaries displayed by preferred term only will be ordered by descending incidence of preferred term. Summaries of the following types will be presented:

- Overall summary of number of unique TEAEs and patient incidence of TEAEs meeting various criteria.
- Overall summary of number of unique SAEs and patient incidence of SAEs meeting various criteria
- Patient incidence of TEAEs by MedDRA system organ class and preferred term
- Patient incidence of TEAEs by CTCAE toxicity grade, MedDRA system organ class, and preferred term.
- Patient incidence of dose-limiting toxicity AEs by MedDRA system organ class and preferred term.
- Patient incidence of TEAEs leading to dose interruption, reduction or discontinuation of valganciclovir by MedDRA system organ class and preferred term.
- Patient incidence of TEAEs leading to reduction or interruption of nanatinostat and valganciclovir by system organ class and preferred term
- Patient incidence of TEAEs leading to discontinuation of nanatinostat and valganciclovir by system organ class and preferred term

- Patient incidence of SAEs by MedDRA system organ class and preferred term.
- Patient incidence of SAEs by CTCAE toxicity grade, MedDRA system organ class, and preferred term.

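### The SAP's DLT list names neutropenia and anemia again in its Grade 4 catch-all, so read literally it counts events that the Protocol's definition leaves out

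*SAP*

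**What the plan says.** Protocol 3.1.5 sets two conditions that every DLT must meet: it falls in the first 28-day cycle of Phase 1b, and it is not beyond dispute due to the lymphoma. At least one further criterion from a list must also be met. In that list anemia, febrile neutropenia and neutropenia each have their own Grade 4 line. Anemia counts as "Grade 4 anemia unexplained by underlying disease", and neutropenia counts only above 5 days. The next line is the catch-all: "Any other Grade 4 hematologic toxicity of any duration".

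SAP 3.4.1.1 repeats the structure. It keeps the condition "Is not incontrovertibly related to underlying disease", the one-criterion rule ("In addition, to be considered a DLT, the AE will meet at least one of the criteria listed below"), the same anemia line and "Grade 4 neutropenia lasting >5 days". Its catch-all, however, reads "Any other Grade 4 hematologic toxicity (thrombocytopenia, neutropenia, febrile neutropenia, anemia) of any duration".

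Both documents allow short events to be left out. The SAP's words are "AEs that persist <72 hours and are able to be managed with supportive care may be excluded".

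The SAP uses the definition in one planned output, listed in SAP 4.5.2: "Patient incidence of dose-limiting toxicity AEs by MedDRA system organ class and preferred term". SAP 3.1.1 refers the reader to Protocol 3.1.5 and to SAP 3.4.1 together, as if they agreed. SAP 1 says that changes from the Protocol's statistical methods will be explained in the SAP. SAP 4.9 lists changes to dosing, central scan review and urine pharmacokinetics, but none to the DLT definition.

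**The concern.** In the Protocol the word *other* does real work. It leaves neutropenia, febrile neutropenia and anemia to their own lines and sweeps up what remains. Once the SAP names neutropenia and anemia inside the catch-all, with no limit on duration, the two narrower lines no longer decide anything for an analyst who follows the list literally. The SAP then conflicts with the Protocol and with itself, because the events it calls *other* are already listed.

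The parenthesis adds nothing for the remaining two events it names. Grade 3 or higher thrombocytopenia and Grade 4 febrile neutropenia are DLTs in both documents anyway. Its only effect is on the two toxicities that carry a limit.

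What is at stake is how a primary safety endpoint is reported. Counts per cohort are small, and under Protocol 3.1.4 one DLT in six patients is acceptable while two are not. A table that differs from the SRC's record by a single patient would be hard to interpret. Protocol 1.7 and 1.9 name neutropenia and anemia as effects of HDAC inhibitors and of valganciclovir, so the affected events are plausible ones.

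**Working it through.** No figure in either document depends on the DLT wording, so there is nothing to reproduce. The check applies the two lists as logic.

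**Inputs.** The Protocol list is in Protocol 3.1.5 and the SAP list in SAP 3.4.1.1. The two general conditions are the same in both. For this test the other routes to a DLT (platelet transfusion, a hold longer than 7 days) and the optional exclusion below 72 hours are switched off.

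**Rules for Grade 4 hematologic events that meet the general conditions**

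- Protocol: neutropenia >5 days, OR anemia unexplained by disease, OR febrile neutropenia, OR any remaining type.
- SAP, read literally: the same, OR neutropenia of any duration, OR anemia from any cause.
- Neutropenia >5 days is a subset of neutropenia of any duration, so the OR of the two is the wider one. The same holds for anemia, subject to the general condition on disease.

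**Result for nine test events**

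| Grade 4 event in Cycle 1 | Protocol | SAP, literal |
|---|---|---|
| Neutropenia, 2 days | no | **yes** |
| Neutropenia, 4 days | no | **yes** |
| Neutropenia, 5 days | no | **yes** |
| Neutropenia, 6 days | yes | yes |
| Anemia, unexplained | yes | yes |
| Anemia, explained by disease but not incontrovertibly | no | **yes** |
| Anemia, incontrovertibly due to disease | no | no |
| Febrile neutropenia | yes | yes |
| Thrombocytopenia | yes | yes |

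Four of nine differ. With the parenthesis deleted, or reworded to leave out neutropenia and anemia, all nine agree.

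**Which differences are firm.** The 2-day neutropenia lasts 2 × 24 = 48 hours, so it may be excluded under the 72-hour clause if supportive care manages it. The 4-day and 5-day events last 96 and 120 hours, so that clause does not reach them. Some of these are DLTs in both documents by another route. Protocol 5.1.8 holds both drugs for low neutrophils until recovery to Grade 2 or better, and a hold longer than 7 days is itself a DLT criterion. The firm difference is therefore neutropenia of about 3 to 5 days with no other criterion met, plus the one class of anemia.

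**Scale, under assumption.** The documents give no rate for such events. If a proportion r of patients has one, the chance that a cohort of n contains at least one is 1 − (1 − r)^n:

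| r (assumed) | n = 3 | n = 6 |
|---|---|---|
| 5% | 1 − 0.95³ = 14% | 1 − 0.95⁶ = 26% |
| 10% | 1 − 0.90³ = 27% | 1 − 0.90⁶ = 47% |
| 20% | 1 − 0.80³ = 49% | 1 − 0.80⁶ = 74% |

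This is the chance that the two definitions give different patient counts for a cohort, provided the reclassified patients have no other DLT. It is not the chance that a cohort's status changes.

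**The case against.** The strongest reply is that this is a drafting slip. The SAP keeps the >5-day line, the anemia line and the word *other*, and SAP 3.1.1 points to Protocol 3.1.5. A sympathetic reader would treat the parenthesis as a loose gloss on hematologic toxicity and let the specific lines govern. That reading is available. But the SAP gives no rule for preferring it, and its one-criterion rule points the other way, so the ambiguity stands.

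Three stronger readings are tempting, and the documents do not support them.

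- *The anemia exception is gone.* It is narrowed. Anemia incontrovertibly related to disease stays excluded by the general condition, which the SAP retains.
- *The DLT table will count extra events.* The SAP does not say whether the DLT flag is programmed from this list or taken from the investigator or SRC. Several elements need clinical judgment, so a recorded determination is at least as plausible. The table could differ; nothing shows that it will.
- *A dose level would change status.* The SRC declares the MTD and sets the RP2D (Protocol 3.10, 12.3.2). SAP 3.3.1.1 already states the RP2D, and SAP 4.9 describes SRC dose changes in the past tense. The SAP applies no escalation rule and is descriptive. Even on paper, moving from one DLT to two needs a cohort that already has exactly one, with the reclassified event in a different patient.

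It is also fair to say that the frequency is unknown. The single-agent DLTs in Protocol 1.8 include neither neutropenia nor anemia. The SRC may also declare unlisted toxicities as DLTs (Protocol 3.1.5), so its count need not match either list exactly.

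**Conclusion.** The point holds as an undeclared conflict in the definition of a primary safety endpoint. On the literal wording, the SAP counts Grade 4 neutropenia of about 3 to 5 days, and Grade 4 anemia explained by disease short of the incontrovertible standard, where the Protocol definition does not. Four of nine test events differ, or three if the short-event exclusion is applied to the 2-day neutropenia.

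The consequence is confined to reporting: the DLT incidence table could disagree with the SRC's record, but past MTD or RP2D decisions would not change. The conclusion on wording rests on the two lists alone. How many patients are affected rests on rates that the documents do not give, so the percentages above show scale only. No view is taken on which clinical threshold is right.

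**What to change.** Reconcile SAP 3.4.1.1 with Protocol 3.1.5 so that one DLT definition applies. State in SAP 4.5.2 that the DLT table uses the definition and the DLT determinations on which the SRC based its escalation decisions. If the wider SAP wording is intended, list it in SAP 4.9 as a change from the Protocol and show DLT counts per cohort under both definitions.

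The cost is about one line of wording, one sentence on the source of the DLT flag and, if both counts are shown, one extra table. No new data are needed. SAP 1 has the SAP finalized before database lock, so the change belongs before that point.
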